### **8.11 Adverse Events**

AEs must be assessed and recorded as specified in Section 9.

### **8.12 Other Safety Assessments**

Local Skin Reactions (LSRs) Assessment of local skin reaction in the treatment area using the LSR Grading Scale will be performed as specified in Section 8.1. Local skin reactions are defined as erythema, flaking/scaling, crusting, swelling, vesiculation/pustulation, and erosion/ulceration. The presence/absence and grade of each LSR will be recorded using the LSR Grading Scale shown in Appendix 2: Local Skin Reaction Grading Scale. Any local skin responses identified within the treatment area which do not match the criteria in the LSR Grading Scale should be reported as AEs.

### **8.13 Patient Reported Outcomes**

The subject must make self-assessments at visits specified in the schedule of trial procedures (Section 8.1). Patient reported outcome measures should be completed prior to other assessments on the day of completion of the questionnaire. The subjects should be encouraged to answer all questions in the questionnaire.

#### EQ-5D-5L

EQ-5D-5L is a standardized generic measure of health related quality of life (11). The questionnaire asks about overall health today in 5 dimensions: mobility, self-care, usual activities, pain/discomfort and anxiety/depression. The health profiles are associated with utilities that are often derived from the general population and that can be used to calculate Quality-Adjusted-Life-Years.

#### Treatment Satisfaction Questionnaire for Medication (TSQM)

TSQM v.9 is a generic questionnaire measuring subjects' satisfaction with the treatment (12). The questionnaire will ask questions relating to effectiveness, side effects, convenience and overall satisfaction.

### **8.14 Investigator Assessments**

#### Identification of the treatment area

At Visit 1, identification of the treatment area should be documented on a study transparency using three-point landmark technique (See Appendix 1: Identifying and Documenting the Treatment Area). The treatment area must be one contiguous area or two non-contiguous areas up to a maximum size of 100 cm^2. At all subsequent visits, the transparency should be used to re-identify the treatment area for assessment of the treated skin.

#### MC count in the treatment area

The number of clinically typical and visible MCs present in the treatment area will be counted at Visit 1 (baseline MC count) and at subsequent visits as specified in the schedule of trial procedures (Section 8.1).

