## 5 Trial Endpoints

### 5.1 Primary Endpoint

- Complete clearance at Week 4, defined as no clinically visible MCs in the treatment area

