### 5.2 Secondary Endpoints

- Partial clearance at Week 4, defined as at least 50% reduction in the number of clinically visible MCs in the treatment area

- Percentage of subjects who sustain complete clearance of MCs in the treatment area at Week 24
- Percentage of subjects who clear MCs outside of the treatment area at Week 24

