## 6 Trial Design

### 6.1 Overall Trial Design

This is a case series in subjects with MC in the setting of immunocompromised status.

Subjects will attend a screening visit where they will be assessed for eligibility. Eligible subjects will complete the baseline visit on the same day as the screening visit. There will be no washout period in this trial. Eligible subjects will be assigned Picato 0.05% gel at Visit 1. Two boxes, each containing 2 tubes of Picato 0.05% gel, will be dispensed to each subject at Visit 1. Subjects should use a new tube for each treatment day.

All subjects will apply gel using a cotton swab for 3 consecutive nights at home (Day 0, Day 1, Day 2). Subjects will be followed for 4 weeks after the first application of IP at Day 0 (3-day treatment period including 4-week follow-up period).

Subjects who have not achieved complete clearance in the treatment area at Week 4 will receive a second course of treatment for 3 consecutive nights (Day 28, Day 29, Day 30). These subjects will be followed for another 4 weeks after the first application of the second course of IP at Day 28 (3-day treatment period including 4-week follow-up period).

Subjects who have not achieved complete clearance in the treatment area at Week 8 will receive a third course of treatment for 3 consecutive nights (Day 56, Day 57, Day 58). These subjects will be followed for another 4 weeks after the first application of the third course of IP at Day 56 (3-day treatment period including 4-week follow-up period).

Residual erythema may be present and will not be considered lesions. All subjects will have follow-up visits at Week 16, Week 20, and Week 24 from the first application of IP.

The number of MCs within the treatment area and outside of the treatment area will be counted at every visit. The treatment area may be one contiguous area or up to two non-contiguous areas. The total treatment area should not exceed 100 cm^2. Picato gel should be applied at least 2 hours before sleeping and be allowed to dry for at least 15 minutes after application. For subjects who cannot tolerate Picato 0.05% gel as judged by the sub(investigator), the lower concentration of 0.015% will be used. The treatment area will be identified and tracked with a transparency, which will capture both anatomical landmarks and the treatment area, to orient the patient and investigator to the treatment area over time.

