### 7.2 Inclusion Criteria

1. Signed and dated informed consent has been obtained.
2. Male or non-pregnant female at least 18 years of age.
3. Subject must have an immunocompromised condition due to use of immunosuppressive therapies for cancer or autoimmune disease treatment or prevention of organ transplant rejection or due to an inherited condition that affects the immune system.
4. Subject has at least 10 clinically typical, visible and discrete MCs within a treatment area on either the face and/or trunk. Treatment area is defined as either:
  - One contiguous treatment area of at most 100 cm^2
  - Two non-contiguous treatment areas totaling at most 100 cm^2
5. Subject must be willing to forego any other treatments of MC on the face and/or trunk, including tanning bed use and excessive sun exposure, throughout the duration of the trial.
6. Subject is willing and able to participate in the study as an outpatient, making frequent visits to the study center during the treatment and follow-up periods, and to comply with all study requirements.
7. Female subjects of childbearing potential\* must have a negative urine pregnancy test prior to trial treatment.

\* A female is defined as not being of child-bearing potential if she is postmenopausal (at least 12 months with no menses without an alternative medical cause prior to screening) or surgically sterile (hysterectomy, bilateral salpingectomy or bilateral oophorectomy).

8. Female subjects of childbearing potential must be willing to use effective contraception at trial entry and until the last follow-up visit at Week 24.

Effective contraception is defined as follows:

- Abstinence (when this is in line with the preferred and usual life style of the subject).
- Vasectomized partner (given that the subject is monogamous).
- An intrauterine device.
- Double barrier method defined as condom in combination with diaphragm
- Hormonal contraceptive (oral hormonal birth control, estrogenic vaginal ring, percutaneous contraceptive patches, implants and injectables) for at least one menstrual cycle prior to enrollment.

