### 7.3 Exclusion Criteria

1. Location of the treatment area
  - on the periorbital skin
  - within 5 cm of an incompletely healed wound
  - within 10 cm of a suspected basal cell carcinoma (BCC) or squamous cell carcinoma (SCC).
2. Previous participation in an ingenol mebutate trial.
3. Treatment with ingenol mebutate gel in the treatment area within 6 months or outside of the treatment area within 30 days prior to study treatment initiation.
4. Receipt of the following within 90 days prior to study treatment initiation:
  - interferons or interferon inducers
  - any dermatologic procedures or surgeries within the treatment area
5. Receipt of any topical prescription medications in the treatment area within 30 days prior to study treatment initiation.
6. Lesions in the treatment area have atypical clinical appearance (e.g. giant lesions greater than 5 mm, eczematous lesions, or folliculocentric lesions).
7. Active dermatologic conditions that may confound the diagnosis of MC or would interfere with assessment of treatment, such as scabies, cutaneous lymphoma, or psoriasis.
8. Clinical diagnosis/history or evidence of any medical condition that would expose a subject to an undue risk of a severe AE or interfere with assessments of safety and efficacy during the course of the trial, as determined by the (sub)investigator's clinical judgment.
9. Known history of infection with Human Immunodeficiency Virus (HIV).
10. History of melanoma.
11. History of chronic alcohol or drug abuse within 12 months prior to screening, or any condition associated with poor compliance as judged by the (sub)investigator.
12. Known or suspected allergy or reaction to any component of the IMP formulation.
13. Patients who have experienced a clinically important medical event within 90 days prior to study treatment initiation (e.g., stroke, myocardial infarction, etc).
14. Pregnant, breastfeeding, or lactating women.
15. Participation in any another interventional clinical trial within 30 days prior to study treatment initiation.

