## 7.6 Withdrawal criteria

Subjects **may** withdraw from the trial for any of the following reasons:

1. *Unacceptable treatment efficacy*: the (sub)investigator is free to withdraw the subject at any time based on a medical judgement.
2. *Unacceptable AEs/LSRs*: any AEs or LSRs that the (sub)investigator or the subject considers unacceptable.
3. *Exclusion criteria*: any exclusion criteria which emerge/become apparent during the subject's participation in the clinical trial.
4. *Voluntary withdrawal*: subjects are free to withdraw from the clinical trial at any time and for any reason. If applicable, the subject's legal representative can withdraw the subject from the trial.
5. *Other reasons*: other reasons than stated above which require the subject to (be) withdraw(n) should be specified.
6. *Lost to follow-up*.
7. *Death*.

Subjects who are discovered, after enrollment, not to have fulfilled all in- /exclusion criteria at the time of enrollment should discontinue treatment unless the (sub)investigator, based on clinical and ethical evaluation, finds discontinuation inappropriate.

Subjects who discontinue treatment for any reason should remain in the trial until Week 24. All subjects should as a minimum be asked to complete the final efficacy assessment that correlates with their treatment course (Week 4, Week 8 or Week 12) and the final visit at Week 24. For subjects withdrawn from treatment or trial, AEs should be followed up as described in Section 9. Subjects withdrawn can be substituted.

Reason(s) for discontinuation from IMP and withdrawal from the trial must be recorded in the medical records (lack of efficacy, AE, withdrawal by subject, lost to follow-up, death, other).

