**Panel 2 Schedule of trial procedures: second and third course of treatment**

	Second course of treatment 				Third course of treatment 			
Visit Number	6	7	8	9	10	11	12	13
Week	5	6	7	8	9	10	11	12
Day	35	42	49	56	63	70	77	84
Visit Window	±3 days	±3 days	±3 days	±3 days	±3 days	±3 days	±3 days	±3 days
Informed consent								
Inclusion/Exclusion								
Demographics								
Medical history								
Medication history								
Vital signs								
Height and weight								
Physical examination 					X			X
Urine pregnancy test 	X	X	X	X	X	X	X	X
Dermatological Assessment (Diagnosis)								
MC lesion count	X	X	X	X	X	X	X	X
LSR assessment	X	X	X	X	X	X	X	X
Adverse event(s)	X	X	X	X	X	X	X	X
Concomitant medications/procedures 	X	X	X	X	X	X	X	X
PROs and Questionnaires 					X			X
Subject instruction/Diary review	X	X	X	X	X	X	X	X
Dispense medication/diary				X 				
Collect medication/diary	X				X			
Assess subject compliance	X	X	X	X	X	X	X	X

- 1) Screening and baseline visit will be done on the same day. There will be no washout period.
- 2) Abbreviated physical examination including general appearance, regional lymph nodes and dermatologic examination of the skin.
- 3) Only female subjects of child-bearing potential.

- 4) At Visit 1, procedures should be recorded as Medical/Surgical History.
- 5) Patient reported outcomes (PROs) and questionnaires include EQ-5D-5L and TSQM v.9.
- 6) Additional IP will be dispensed at Week 4 and/or Week 8 for subjects who have incomplete clearance of MC in the treatment area.
- 7) A second course of treatment is warranted only for subjects who have incomplete clearance MC in the treatment area at Week 4.
- 8) A third course of treatment is warranted only for subjects who have incomplete clearance MC in the treatment area at Week 8.
- 9) For unscheduled visits, only assessments that require follow-up will be conducted.

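### Protocol 8.14 counts only typical-looking visible MCs at follow-up, but 5.1 and 5.2 define clearance on all visible MCs; taken literally, the gap can only favour complete clearance at a given visit

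*Protocol*

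**What the plan says.** The protocol describes the lesions that matter for efficacy in three ways.

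- **Endpoints.** Section 5.1 sets the primary endpoint: "Complete clearance at Week 4, defined as no clinically visible MCs in the treatment area". Section 5.2 sets partial clearance at Week 4 as "at least 50% reduction in the number of clinically visible MCs in the treatment area". Neither requires a lesion to look typical.
- **Counting rule.** Section 8.14, the only section that spells out the treatment-area count, says that "clinically typical and visible MCs present in the treatment area will be counted at Visit 1 (baseline MC count) and at subsequent visits". The restriction to typical lesions therefore applies at follow-up as well as at baseline.
- **Unqualified wording.** Section 6.1 says that MCs inside and outside the treatment area are counted at every visit, and the schedule in 8.1 lists an MC lesion count. Neither adds a qualifier. The only finding that 6.1 sets aside is erythema: "Residual erythema may be present and will not be considered lesions".

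Typical appearance also serves as an entry requirement. Inclusion criterion 4 in 7.2 reads "Subject has at least 10 clinically typical, visible and discrete MCs within a treatment area on either the face and/or trunk", and exclusion criterion 6 in 7.3 bars subjects when "Lesions in the treatment area have atypical clinical appearance (e.g. giant lesions greater than 5 mm, eczematous lesions, or folliculocentric lesions". No section says how a visible MC that is atypical after treatment is to be scored.

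**The concern.** A requirement that suits eligibility has been carried into the outcome count. By the protocol's own examples in exclusion criterion 6, an MC that has grown past 5 mm or become eczematous is atypical. Under 5.1 such a lesion at Week 4 means the subject is not completely cleared. Under a literal reading of 8.14 it is not counted, and if it is the only lesion left the recorded count is zero.

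The mismatch reaches the primary endpoint of a 10-subject series, where one subject is a visible part of the result. It also arises when the data are collected. If a lesion is never counted, no later analysis rule can put it back.

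Complete clearance has a second use. Section 6.1 and the schedule footnotes rely on it at Weeks 4 and 8, for example "A second course of treatment is warranted only for subjects who have incomplete clearance MC in the treatment area at Week 4". Those statements inherit the same ambiguity.

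**Working it through.** The protocol states no figure to reproduce: N = 10 in 6.2 is given without a calculation. The check is therefore one of logic, with small examples.

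**Notation.** For one subject at one visit, T is the number of typical and visible MCs in the treatment area (8.14), A the number of visible but atypical MCs, and V = T + A the number of visible MCs (5.1, 5.2), with A ≥ 0. Subscript 0 is baseline and 4 is Week 4.

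**1. Complete clearance.** Success under 5.1 is V4 = 0; success on the 8.14 count is T4 = 0.
- V4 = 0 forces T4 = 0, so a 5.1 success is always an 8.14 success.
- T4 = 0 with A4 = 1 gives a count of 0 under 8.14 and 1 under 5.1: a success on one and a failure on the other.
- Enumeration over T0 = 10 to 20, A0 = 0 to 5, T4 = 0 to 20 and A4 = 0 to 10 gives 11 × 6 × 21 × 11 = 15,246 combinations. They agree in 14,586. In 660 (11 × 6 × 10, those with T4 = 0 and A4 ≥ 1) only the 8.14 count shows success. None go the other way.

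**2. Partial clearance.** Success on the 8.14 count is T4 ≤ 0.5 × T0; success under 5.2 is T4 + A4 ≤ 0.5 × (T0 + A0).
- With A0 = 0, as exclusion criterion 6 intends, success under 5.2 implies T4 ≤ T4 + A4 ≤ 0.5 × T0, so the gap again favours success only. Example: baseline 10 typical; Week 4, 5 typical and 1 atypical. On 8.14, (10 − 5)/10 = 50%, a success. Under 5.2, (10 − 6)/10 = 40%, a failure. Of the 11 × 21 × 11 = 2,541 combinations with A0 = 0, 565 favour success and none go against it.
- With A0 > 0 the direction can reverse. Example: baseline 10 typical and 2 atypical; Week 4, 6 typical and 0 atypical. On 8.14, (10 − 6)/10 = 40%, a failure. Under 5.2, (12 − 6)/12 = 50%, a success. This needs a subject enrolled despite exclusion criterion 6. Section 7.6 allows for such subjects: they "should discontinue treatment unless the (sub)investigator, based on clinical and ethical evaluation, finds discontinuation inappropriate".

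These tallies show direction only. They are not probabilities.

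**3. Sustained clearance at Week 24.** Assume, since the protocol does not say, that the denominator is the subjects clear at Week 4. If 3 of 4 truly sustain clearance (75%) and one further subject is wrongly scored clear at Week 4, the result is 3/5 = 60% or 4/5 = 80%, depending on how that subject is scored at Week 24. The direction is not fixed.

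**4. Size.** Each affected subject moves the complete clearance rate by 1/10 = 10 percentage points. The number affected is not in the protocol. The table assumes 0, 1 or 2 affected subjects and a true 4/10.

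| Affected (assumed) | Reported | Exact (Clopper-Pearson) 95% interval |
|---|---|---|
| 0 | 4/10 = 40% | 12.2 to 73.8% |
| 1 | 5/10 = 50% | 18.7 to 81.3% |
| 2 | 6/10 = 60% | 26.2 to 87.8% |

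**The case against.** The best reply is that the protocol need not be read this way. MC is diagnosed by appearance and confirmed by the (sub)investigator (8.9), so *clinically typical* may mean no more than *recognisable as MC*. An assessor who reads it so, or who works from the unqualified sentence in 6.1 or directly from 5.1, scores correctly. Section 8.14 does not say that the endpoints are derived from its count, and that derivation could sit in an analysis plan that is not among the documents. Exclusion criterion 6 removes atypical lesions at entry, so the gap opens only if a lesion is atypical at follow-up and still identified as MC.

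Much of this stands. It makes the harm conditional and keeps the point modest. It does not remove the inconsistency: 8.14 is the more specific text, it applies expressly to later visits, and the same protocol gives *atypical* a meaning through its examples. An analysis plan can choose among recorded counts but cannot recover a lesion that was left out.

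A reader might also infer that nobody looks at the treated skin at Week 24, because the abbreviated physical examination (8.6) is not scheduled then. The documents do not support that. A local skin reaction assessment of the treatment area is scheduled at Week 24, and 9.1 requires a qualified physician to do it. Neither assessment is an MC count, but a residual lesion could be noticed.

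**Conclusion.** The inconsistency is real and should be corrected, as a modest point. If 8.14 is followed literally and the endpoints are taken from its count, a subject with a visible atypical residual MC can be scored as completely cleared, contrary to 5.1. For that endpoint, in a given subject at a given visit, the reverse cannot happen. For partial clearance the same direction holds when no atypical lesion was present at baseline. For the Week 24 percentage no direction can be claimed.

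The size is 10 percentage points per affected subject. How many would be affected is unknown, and the range of 0 to 2 is an assumption.

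Two stronger inferences are not supported. One is that the protocol instructs assessors to ignore atypical MCs, so that the reported rate will be inflated: 6.1, the schedule and 5.1 carry no such restriction, and no frequency is given. The other is that the trial's conclusion would change: this is an uncontrolled case series, and the intervals above overlap widely.

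**What to change.** Keep the requirement of typical appearance for eligibility (7.2, 7.3 and Appendix 1) and remove it from the outcome count. Section 8.14 could read:

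> At each visit, every clinically visible lesion in the treatment area that the (sub)investigator judges to be MC is counted, whether or not its appearance is typical. Residual erythema is not a lesion (see 6.1). The treatment-area endpoints in 5.1 and 5.2 are derived from this count.

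Section 6.1 and the schedule footnotes, which use complete clearance at Weeks 4 and 8, must be reconciled with 5.1 and 8.14 so that the term has one meaning throughout. No rule on further treatment is proposed here.

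The cost is a short text change and a matching label on the source form, with no added visit or procedure. The downsides are a possibly slightly lower clearance rate and the need for the (sub)investigator to judge whether an atypical lesion is MC.

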### **8.15 IP Dosing Diary and Subject Instruction**

Subject will be required to maintain an IP dosing diary to record the date and time of IP application. Subject will be provided with a Patient Safety and Study Instruction Sheet at baseline.

### **8.16 Dispensing and Returning of IP**

Refer to Section 10.6.

## **9 Adverse Events**

- AEs and SAEs are defined in Appendix 3: Definitions of Adverse Events and Serious Adverse Events.
- Classification of AEs in terms of severity, causality and outcome are defined in Appendix 4: Classification of Adverse Events.

### **9.1 Collection of Adverse Events**

All AEs and SAEs must be collected from the signing of the informed consent form and until the last follow-up visit at Week 24.

Abnormal findings observed at screening do not constitute AEs, but must be recorded in medical history.

For AEs recorded on the day starting treatment, it should be specified whether the AE started prior to or after first application of IP.

AEs must be assessed by medically qualified personnel. A qualified physician must conduct all dermatologic examinations, LSR and AE evaluation of the treatment area.

At all visits, the subject will be asked a non-leading question by the (sub)investigator such as: “How have you felt since I saw you last?” No specific symptoms should be asked for. It is important that the (sub)investigator also observes the subject for any changes not reported by the subject and records these changes.

### **9.2 Reporting of Adverse Events**

AEs reported by the subject or observed by the (sub)investigator must be recorded on the AE form and should be described in the following manner:

The AE term will be in precise English medical terminology (i.e. not necessarily the exact words used by the subject). Whenever possible, a specific diagnosis should be stated (e.g. allergic contact dermatitis).

For AEs the location must be part of the AE description and may be described as “in the treatment area”, “outside the treatment area” or “non-cutaneous”.

The duration of the AE must be reported by the start date and stop date of the event. In addition, it must be recorded whether the AE started prior to start of trial medication.

AEs must be classified in terms of severity, causality and outcome according to the definitions in Appendix 4: Classification of Adverse Events.

